### **Statistical Considerations**

#### **Power and Sample size:**

We propose to test the primary hypothesis that rates of smoking cessation will be significantly higher 6-months after lung screening for the smoking cessation strategy involving a gain-framed intervention + 2 weeks of nicotine patches and lozenges compared to a strategy of an unframed behavioral intervention + no medication. We assume a biologically confirmed 7-day point prevalence abstinence rate at the 6 month follow up visit of 10-13% for the participants randomized to receive no NRT or gain framed messaging based on USPHS guidelines (Table 6.7 and 6.8 of USPHS Guidelines). In studies with a similar 2 week NRT exposure, 6 month abstinence rates varied from 16-34 % and a conservative estimate of a 20% abstinence rate in those receiving NRT only will be assumed. Based on previous work we estimate that the abstinence rate of in those receiving both NRT and gain framed messaging will be 10-11% increased over those with unframed messaging. Based on these estimates, we will have 80% power with a type 1 error rate of 5% to detect the conservative difference of between those receiving gain framed messaging + NRT (28%) and those receiving unframed messaging and no NRT (13%) with 123 participants randomized to each of the 4 treatment groups (total n=492 Participants). This assumes that the two treatment sites are moderately correlated (ICC=0.85) and randomize equal numbers of patients to each treatment cell. Additionally, we anticipate that 15-20% of our participants will fail to report 6 month follow up outcome data (LTF, death, moved out of area), accounting for a 20% attrition during the study follow up, we would need to randomize **n=367 participants** across all sites (179 randomized at Yale and 179 between MUSC and the VA) to maintain adequate power to detect the clinically meaningful difference stated. Assuming an abstinence rate of 14-17% in the group receiving unframed messages, we will have >80% power with a type 1 error rate of 5% to detect an 11% increase in abstinence in those receiving gain framed messages with the sample size stated for aim 1. We considered but opted against powering our trial on the treatment interaction, as this would require >5,000 participants.

Anticipated abstinence rates – 6 months	Gain-framed Intervention	No Message Intervention	
2 week starter pack NRT	28-30%	18-20%	23-25%
No Medication	20-23%	10-13%	15-18%
	24-27%	14-17%	

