### **Design and Methods:**

#### **General overview:**

We propose a group comparison study (gain-framed intervention vs. unframed intervention, starter package of 2 weeks of nicotine patches and lozenges vs. no medication) to evaluation methods to boost rates of smoking cessation for a high-risk group of smokers (N=367) with varying levels of motivation across 3 study sites (MUSC, Ralph H. Johnson Veteran Administration and Yale). All eligible study participants will be randomized to receive either: 1) Unframed Messaging (hereafter referred to as UM) with no medication, or 2) Gain-framed Messaging + Meds (i.e., 1 gain-framed video and print materials + 2 week starter pack of NRT; hereafter referred to as GM+M).

**Participants:** Our target sample will be 367 lung screening patients who currently smoke at each of 3 study sites: MUSC), Ralph Johnson VA, and Yale Cancer Center); Total N=367. The following eligibility criteria will ensure that we obtain our study sample of lung screening patients. **Inclusion:** 1) 50 years or older (we see no reason for an upper limit given supportive evidence for cessation among elderly), 2) at least a 20 pack year history of smoking (i.e., the base population of high risk smokers to get screened) as assessed by the patients ordering healthcare provider or the research team, 3) current smoker (defined as any smoking in the past 30 days – this is the criteria our lung cancer screening programs will use to trigger tobacco treatment interventions), 4) willing to be randomized, 5) English speaking; **Exclusion:** 1) unstable psychiatric/medical conditions such as suicidal ideation, acute psychosis, severe alcohol dependence, or dementia, and 2) known allergy to adhesives, and 3) current participation in another tobacco treatment program (e.g., using medication from a primary care doctor, quitline, etc).

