**NRT sampling:** Participants in the medication arm (GM+M) will be given a 2-week long supply of both nicotine patch and lozenge. NRT samples will be delivered in addition to all standard care treatment described above. Given the very brief 'intervention' time (few minutes), we believe that treatment groups will be essentially time-matched. We will provide a 2-week supply of both 4 mg lozenge and 21mg nicotine patches provided in the original packaging. Detailed information on each product, including instructions for use, will be provided in the take-home packet, which will include FAQs and related information intended to dispel medication misperceptions. Patients who are receiving nicotine patches and lozenges will be given the option to try these over-the-counter products (i.e., a patch and a lozenge) at the time of their study visit with aid from the research staff and will receive handouts and instructions about proper use of the NRT. We provide both patch and lozenge for four reasons. **First**, a number of studies demonstrate their efficacy when used singularly. **Second**, they are both over the counter, increasing their utility in various populations, particularly within lung cancer screening settings where eligibility is minimal and instructions on use require nominal discussion. **Third**, whereas the patch provides a steady dose of nicotine throughout the day, the lozenge is used ad libitum and provides acute nicotine administration. These two mechanisms might appeal to smokers differently. **Fourth**, two studies have shown that combined use of patch + lozenge is superior over placebo and single NRT products. We neither explicitly advise nor discourage combined use. Thus, this is an opportunity for smokers to learn about two NRT products, to be used individually or together (participant choice, including none at all). We will caution all participants on signs of receiving too much nicotine (nausea, dizziness), and will monitor adverse events, expected to be rare/mild. Given our inclusive study criteria, some study participants who have low nicotine dependence will receive the starter package of NRT. However, given recent evidence that dual NRT benefits most low dependence smokers, we feel this is appropriate. We do not offer a placebo comparison because we are interested in the provision of medication vs. not (and not to determine if effects are pharmacologic). However, participants not receiving the starter kit of NRT will still be advised to use evidence based medications, including NRT, per standard guidelines. The NRT for MUSC patients will be stored in a cabinet in the Tobacco Treatment Program offices. The door to the office suite locks. The NRT for VA patients will be obtained via the research pharmacy at the Ralph H Johnson VA Medical Center.

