#### **Statistical Analysis:**

Categorical clinical and demographic variables will be assessed by chi-square tests of independence, while continuous variables will be assessed using Student's *t*-test. In addition to baseline group differences, preliminary analysis of baseline characteristics with outcomes of interest will examine significant correlates of abstinence in the study population. Characteristics found to be significantly associated with smoking outcomes will be included as covariates in the initial stages of model development. *Our primary aim is to determine if the rate of smoking cessation among lung screening patients may be improved by delivering gain-framed smoking cessation messages and delivery of a free starter package of medication (gain-framed behavioral intervention + 2 weeks of nicotine patches and lozenges vs. unframed behavioral intervention + no medication).* We hypothesize that rates of smoking cessation will be significantly higher at 6-months after lung screening for the smoking cessation

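### The trial randomises to two arms, but the power section and models assume four cells: framing and NRT effects cannot be separated, and 367 neither follows from the stated inputs nor agrees with 616

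*Combined protocol and SAP*

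**What the plan says.** **Design.** The General overview states: "All eligible study participants will be randomized to receive either: 1) Unframed Messaging (hereafter referred to as UM) with no medication, or 2) Gain-framed Messaging" with the NRT starter pack, N=367. The NRT sampling text agrees: "Participants in the medication arm (GM+M) will be given a 2-week long supply of both nicotine patch and lozenge". The primary contrast in Statistical Analysis is the same two-group comparison: "gain-framed behavioral intervention + 2 weeks of nicotine patches and lozenges vs. unframed behavioral intervention + no medication".

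**Power and Sample size.** This section gives 80% power at a 5% type 1 error rate for 28% against 13% "with 123 participants randomized to each of the 4 treatment groups (total n=492 Participants"). Then, "accounting for a 20% attrition during the study follow up, we would need to randomize" 367, split by site as "179 randomized at Yale and 179 between MUSC and the VA". It adds: "This assumes that the two treatment sites are moderately correlated (ICC=0.85"). For framing, it claims: "we will have >80% power with a type 1 error rate of 5% to detect an 11% increase in abstinence in those receiving gain framed". The stated comparator rate is 14-17% with unframed messages. The table of anticipated rates has four cells with row and column margins.

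**Models.** Statistical Analysis puts framing and NRT into the primary and secondary models as two separate randomised conditions, and describes its Cox models as 2x2. Specific Aims says that the study is powered for the main effects of both interventions. Significance describes a 2x2 basis with interactions explored.

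**Enrolment.** Human Subjects Involvement and Characteristics gives 616. Specific Aims, the General overview, Power and Sample size, and the timeline give 367.

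**The concern.** The design is written for two arms and the statistics for four cells. If a participant has either both interventions or neither, the framing and NRT indicators are one and the same variable. Software given both terms will drop one, and the coefficient that remains is the effect of the package. A report that followed the plan literally could label that coefficient as framing or as NRT.

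The protocol also credits the trial with powered tests of each component, which its randomisation cannot supply. The sample size is presented as an inflation for attrition, yet 367 is smaller than the 492 that it should inflate. A reader therefore cannot tell what 367 was designed to detect, or whether the target is 367 or 616.

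**Working it through.** **Inputs (Power and Sample size):** 28% v 13%; 123 per group; 4 groups; 5% type 1 error; 80% power; 20% attrition; framing control rate 14-17% with an 11-point gain. Sidedness is not stated, so I take two-sided unless noted.

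**Formula (pooled normal test, n per arm):** power = Φ{[|p1−p2|√n − 1.96·s0]/s1}, where s0 = √[2p̄(1−p̄)] and s1 = √[p1(1−p1)+p2(1−p2)].

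**1. The plan's 123 per group.** For 28% v 13%, p̄ = 0.205, s0 = 0.5709, s1 = 0.5610.
- n per arm for 80% power is 113 (126 with continuity correction).
- At n = 123: Φ{[0.15×11.09 − 1.96×0.5709]/0.5610} = Φ(0.97) = 83.4%. Fisher's exact test gives 79.8%.

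So 123 is a sound size for this contrast.

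**2. From 123 to the number randomised.**
- Four cells: 4×123/0.80 = 492/0.80 = 615. Rounding per cell, 123/0.80 = 153.75, so 154, and 4×154 = 616, the figure under Human Subjects Involvement and Characteristics.
- Two arms: 2×123/0.80 = 307.5, so 308.
- To reach 367 from 246 would need attrition of 1 − 246/367 = 33%, against the stated 15-20%.
- Another pair in the table, 28% v 10%, needs 73.37 per cell, and 4×73.37/0.80 = 366.9. That may be where 367 came from, but it is not the stated pair and it is still four cells.
- Site split: 179+179 = 358, not 367.

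**3. Identifiability.** In two arms the rows of (intercept, framing, NRT) are (1,0,0) and (1,1,1). The rank is 2 of 3; with the interaction it is 2 of 4. With all four cells the main-effects matrix has full rank, 3 of 3.

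**4. The framing claim.** The 14-17% is the unframed column averaged over NRT and no NRT: (18+10)/2 = 14 and (20+13)/2 = 16.5. Two arms have no such margin. The table shows what the claim needs.

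| n per margin | 14% v 25% | 17% v 28% |
|---|---|---|
| 246 (492 in four cells) | 87.1% | 83.4% |
| 183.5 (367 in four cells) | 76.0% | 71.5% |
| 183.5, one-sided | 84.7% | 81.2% |

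The statement of more than 80% fits the 492-person factorial. At 367 in a factorial it would hold only one-sided. With 367 in four cells (91.75 each), 28% v 13% would have 71.4%.

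**5. Primary contrast in two arms.** Statistical Analysis counts missing participants as non-abstinent. If 20% are missing and none would count as abstinent, the rates become 28×0.8 = 22.4% and 13×0.8 = 10.4%.

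| Randomised | 28% v 13% | 22.4% v 10.4% |
|---|---|---|
| 367 (183.5 per arm) | 94.8% | 87.7% |
| 358 (179 per arm) | 94.3% | 86.9% |

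By Fisher's exact test at 184/183 the figures are 94.0% and 85.9%. None of these figures includes a site correlation, because the plan gives no formula by which the ICC of 0.85 enters.

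**6. Accrual.** The timeline gives about 14 per month over months 7-51, which is 45 months, and 14×45 = 630. That is close to 616. Recruiting 367 at 14 per month takes 26.2 months.

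**The case against.** The strongest reply is that the documents do not settle the two-arm reading. Specific Aims describes a framing by NRT layout at N=367. The intake text treats the NRT group and the gain-framed group separately, Gain-Framed Messaging and the exploratory aims use plural groups or arms, and Safety Monitoring allows one intervention or both. This is version 13, and the text does not say whether anyone was allocated to four cells. If some were, the two factors would be at least partly estimable, and a single GM+M versus UM term would leave single-intervention participants without a place in the model.

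That stands as a reason to confirm the allocation first and to make the model change conditional on the answer. It does not rescue the text. The General overview covers all eligible participants and is explicit. A four-cell trial of 367 would still miss the two-sided power claims, and 616 would still conflict.

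Two smaller points also stand. The power figures ignore site correlation, although stratifying randomisation by site should limit the effect. Fisher's exact test and the continuity-corrected formula sit closer to the stated 80% at 123 than the uncorrected normal test does, so the sponsor must name its method. The primary hypothesis is already a two-group contrast, so the damage falls on the models, the component claims and the stated size, not on the main test.

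**Conclusion.** The point holds and must be fixed: the plan is wrong as written. Under the two-arm randomisation in the General overview, separate framing and NRT effects and their interaction are not estimable at any sample size, so the framing power statement and the two-factor models cannot apply. The 367 does not follow from the stated inputs (615 for four cells, 308 for two arms) and contradicts 616.

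The primary contrast is adequately powered: about 95% at 367, or about 88% with dilution by 20% attrition. Those two figures assume equal arms, a pooled normal two-sided 5% test, rates of 28% and 13%, and no site clustering. Confidence is high that the sections contradict one another. That no component effect can be estimated depends on everyone being allocated to the two arms.

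**What to change.** 1. Confirm that every participant is randomised to UM or GM+M. If anyone was allocated to four cells, state the numbers and set the power and model for that. The remaining model and claim changes apply if two arms are confirmed.
2. Restate Power and Sample size for two arms, naming the test and its sidedness. With a pooled normal two-sided 5% test of 28% v 13%: about 83% at 123 per arm, about 95% at 367 randomised, and about 88% at 367 with rates diluted to 22.4% v 10.4%. Give the rationale for 367.
3. Delete the framing power sentence and the four-group basis of 492. Withdraw the main-effect power and interaction claims in Specific Aims and Significance.
4. In Statistical Analysis, replace the two-factor models, including the 2x2 Cox models, with one treatment term (GM+M v UM), and keep the site effect.
5. Show how the ICC of 0.85 enters the calculation, or remove it.
6. Use one enrolment total, with a site split and accrual rate that agree with it, in Power and Sample size, the recruitment section and timeline, and Human Subjects Involvement and Characteristics.
7. Align the remaining wording that implies separate groups (intake, Gain-Framed Messaging, exploratory aims, Safety Monitoring).

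The cost is protocol wording and one confirmation of the allocation scheme. No participants, visits or data are added. The trial gives up claims about each component alone, which two arms could not have supported.

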#### **Statistical Analysis:**

Categorical clinical and demographic variables will be assessed by chi-square tests of independence, while continuous variables will be assessed using Student's *t*-test. In addition to baseline group differences, preliminary analysis of baseline characteristics with outcomes of interest will examine significant correlates of abstinence in the study population. Characteristics found to be significantly associated with smoking outcomes will be included as covariates in the initial stages of model development. *Our primary aim is to determine if the rate of smoking cessation among lung screening patients may be improved by delivering gain-framed smoking cessation messages and delivery of a free starter package of medication (gain-framed behavioral intervention + 2 weeks of nicotine patches and lozenges vs. unframed behavioral intervention + no medication).* We hypothesize that rates of smoking cessation will be significantly higher at 6-months after lung screening for the smoking cessation

strategy involving a gain-framed intervention + 2 weeks of nicotine patches and lozenges compared to a strategy of an unframed behavioral intervention + no medication. Primary and secondary models will be developed including the effects of both randomized conditions; gain framed vs. unframed messaging and NRT vs. no medication, and a cluster effect of study site. Models will be computed both unadjusted and adjusted for significant covariates found in the preliminary analysis. For these efficacy analyses, 7-day point prevalence abstinence will be defined as having no cigarettes (or other tobacco products) for 7 days, confirmed by CO breath test less than or equal to 10 ppm. All randomized participants will be included in the analyses (intent-to-treat approach), and participants will be considered non-abstinent at any missed visit (drop-out/lost-to-follow-up included). To comprehensively analyze the longitudinal efficacy of gain framed messages and NRT sampling, the entire study time course will be analyzed with repeated measures logistic regression using a Generalized Estimating Equation framework. Continuous abstinence (CA) from the time of lung screening to the 1 and 3 month follow-ups (Weeks 4 and 12) and to final follow-up visit (Week 26) will be assessed using logistic regression analysis. Time to first lapse (puff) and time to relapse (first of 3 consecutive days smoking  $\geq 1$  cigarette) will be analyzed using Cox Proportional Hazard models with effects of both randomized conditions in a 2x2 design; gain framed vs. unframed messaging and NRT vs. no medication, and a cluster effect of study site. In addition to the primary intent-to-treat analyses, additional exploratory approaches (e.g., modified intent-to-treat models, per protocol analysis, and completer analysis) will be undertaken as indicated and a sensitivity analysis comparing these models to the ITT model will be completed.

*We have an exploratory aim in which we plan to examine moderators of treatment to determine which subgroups are most likely to respond to the gain-framed and medication interventions, and we will explore differential effects of the study factors across treatment groups.* Procedures from MacKinnon et al. will be used to test mediators. We hypothesize that changes in self-efficacy, smoking cessation outcome expectancy, familiarization with NRT, motivation, and autonomy will act as mechanisms for the smoking cessation effects (i.e., will act as mediators of treatment). Variables that predict the outcome variable (smoking cessation) differently between treatments will be considered to be moderators using the model outlined by Kraemer et al. In order to be considered a moderator, the variable must be present prior to randomization and must not be related to the independent variable. We hypothesize that lung screening findings (e.g., presence of a nodule, cancer, etc.), nicotine dependence, and health disparities will modify treatment response (i.e., will act as baseline moderators of treatment). Variables that predict the outcome variable but do not significantly interact with treatment condition (i.e., influence outcome regardless of treatment condition) will be classified as nonspecific pre-randomization predictors.

*Our other exploratory aim will examine additional treatment endpoints: patient reach, intervention fidelity, patient acceptance and engagement, cost, and the ease of delivery and feasibility.* We hypothesize that we will reach a majority of qualified patients who are current smokers, adherence to the critical elements of the intervention design and delivery methods will be successfully met, patient acceptance and engagement will be greater in the gain-framed messaging and NRT arms, the cost will be higher in the NRT arms, and both the gain-framed messages and dispensing of the 2-week starter pack of NRT will be easily delivered and feasible as part of the lung screening clinic work flow. Patient adherence, exposure to study content, acceptance/responsiveness to content and noted distinguishing factors will be assessed within the study and across study groups. Associations between treatment status and these exploratory endpoints will be assessed using general linear mixed models with data appropriate residual distribution assumptions (Gaussian, Poisson, etc.) and transformations where necessary.

Adverse Events (AE) and Serious Adverse Events (SAE) will be recorded during the duration of the treatment period. All cause treatment emergent adverse event and serious adverse event frequencies will be compared through the use of analysis of variance models. Of particular interest will be (S)AEs that lead to treatment suspension or study discontinuation. Study retention will be assessed by two methods; total number of treatment visits attended will be compared using Poisson regression for count data, while the number of days retained will be assessed using Cox Proportional Hazards regression models.

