Our group has established effective tobacco interventions that demonstrate increased quit attempts and smoking cessation from: 1) gain-framed messaging, and 2) nicotine replacement therapy (NRT) sampling. Based on the tenets of Prospect Theory and an accumulating body of evidence from our previous studies, messages emphasizing the benefits of smoking cessation (i.e., gain-framed) are more effective than messages emphasizing the risks of continued smoking (i.e., loss-framed) for increasing intentions to quit, quit attempts, and smoking cessation in general populations of smokers. Our work also includes several studies showing that sampling of cessation medications leads smokers (both motivated and not) to increased cessation. Together, gain framed messaging and NRT sampling offer a novel and compelling opportunity to engage smokers and catalyze cessation. Our methods, if shown to be successful, can be easily shared with lung cancer screening programs across the country. Thus, we plan to conduct a randomized trial of gain-framed intervention (yes vs. no) x NRT sampling (2-week supply of both nicotine patch and lozenge vs. not) within a high-risk group of smokers (N=367) across 3 study sites (MUSC, VA and Yale). This study is powered to examine main effects of our 2 interventions:

**Primary Aim 1:** *To determine if the rate of smoking cessation among lung screening patients is improved by delivering gain-framed smoking cessation messages and delivery of a free starter package of medication (gain-framed behavioral intervention + 2 weeks of nicotine patches and lozenges vs. unframed behavioral intervention + no medication).*

**Hypothesis 1:** Cessation rates will be significantly higher at 6-months after lung screening for the smoking cessation strategy involving a gain-framed intervention + 2 weeks of nicotine patches and lozenges compared to a strategy of an unframed behavioral intervention + no medication. We define cessation as 7-day point prevalence but will assess multiple definitions of success.

**Exploratory Aim:** *To examine mediators and moderators of treatment to determine mechanisms of treatment effects and which subgroups are most likely to respond to the gain-framed and medication interventions, and to explore differential effects of the study factors across treatment groups. Treatment interactions will also be explored secondarily.*

[figure not shown]

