**Hypothesis:** Changes in self-efficacy, smoking cessation outcome expectancies, familiarization with NRT, motivation, and autonomy will act as mechanisms for the smoking cessation effects (i.e., will act as mediators of treatment). Lung screening findings (e.g., presence of a nodule, cancer, etc), nicotine dependence, and health disparities will modify treatment response (i.e., will act as baseline moderators of treatment).

**Exploratory Aim:** *To examine additional treatment endpoints: patient reach, intervention fidelity, patient acceptance and engagement, cost, and the ease of delivery and feasibility.*

**Hypothesis:** We hypothesize that this project will be a low-cost feasible intervention that will reach a majority of patients who are smokers, with high adherence to and acceptance of the critical intervention elements.

Our rigorously designed study will be the first to demonstrate the individual and combined effects of gain-framed messaging and NRT sampling in a lung cancer screening population, which is a high-risk, difficult to

treat group of smokers in need of feasible, easily administered interventions, thus offering strong potential for clinical and population impact.

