#### Study Interventions:

Gain-Framed Messaging: We will develop 1 gain-framed video and corresponding printed materials. The video will be approximately 4 minutes long and will include individuals of differing racial and ethnic backgrounds representative of our study population. The video will be designed specifically for lung screening patients, addressing how quitting smoking can be helpful given their present situation. To be clear, we are not framing any information to encourage lung screening – the gain-framed intervention will focus on smoking cessation in the context of lung screening. It will highlight [name] recent paper showing that quitting smoking will significantly reduce their risk for lung cancer in conjunction with screening. For example, a gain-framed statement in this regard might say: "Attending this lung screening visit and low-dose CT screen is a great step toward better health and reducing your risk of lung cancer. Even if you decide not to undergo screening, you can still further reduce your risk of developing lung cancer and other diseases by quitting smoking. Research of high risk people who did not have a CT scan shows that by quitting smoking and maintaining abstinence you continue to reduce your risk for lung cancer."

For those in the arm that will receive gain-framed materials, we will disseminate the gain-framed print media to patients at the time of intake. A research assistant will show participants their assigned video via an iPad if they are assigned to the GM+M groups. We chose these procedures for several reasons: a) delivering the gain-framed messages by video allows us keep the content consistent, b) videos are easily disseminable, c) having our research staff administer the videos is consistent with how the videos would be administered at other lung screening programs (i.e., given by support staff and not clinicians), and d) this does not necessitate any special training or procedures with the clinical staff.

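### The plan randomises to two arms but models framing and NRT as two separate effects, which a two-arm design cannot estimate

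*Combined protocol and SAP*

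**What the plan says.** **Allocation.** Under General overview: "All eligible study participants will be randomized to receive either: 1) Unframed Messaging (hereafter referred to as UM) with no medication, or 2" being gain-framed messaging with the NRT starter pack (GM+M). Study Interventions ties both components to that one arm. For the video: "A research assistant will show participants their assigned video via an iPad if they are assigned to the GM+M groups". For the medication: "Participants in the medication arm (GM+M) will be given a 2-week long supply of both nicotine patch and lozenge".

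**Primary question.** Primary Aim 1, the Power and Sample size section and the Statistical Analysis section all compare the combined package with neither component.

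**Models.** Statistical Analysis specifies: "Primary and secondary models will be developed including the effects of both randomized conditions; gain framed vs. unframed messaging and NRT vs. no medication", with a cluster effect of site. The Cox models for lapse and relapse have "effects of both randomized conditions in a 2x2 design". On the analysis set: "All randomized participants will be included in the analyses (intent-to-treat approach".

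**Claims.** Specific Aims states "This study is powered to examine main effects of our 2 interventions" and that the study "will be the first to demonstrate the individual and combined effects of gain-framed messaging and NRT sampling". The Significance section calls the design 2x2. Power and Sample size uses four groups of 123, gives a four-cell table of rates with margins, and claims more than 80% power for a framing main effect. The exploratory aims refer to NRT arms in the plural. The Data and Safety Monitoring Plan describes receiving messages and/or NRT. The Human Subjects section plans 616 participants, against 367 elsewhere.

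**The concern.** With only UM and GM+M, nobody receives framing without NRT or NRT without framing. The two treatment variables are then one variable entered twice. No analysis of those data can divide the package effect between its components, and the interaction is not estimable either.

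The stated primary hypothesis is not lost, because a single indicator estimates it. But the models named for the primary and secondary analyses are not that model, and fitting them as written leaves the output to the software. Some routines stop. Others print separate framing and NRT odds ratios with confidence intervals, which look like the component results that Specific Aims promises.

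The documents also do not say whether anyone was randomised to a single-factor arm under an earlier version. If so, the two-term model can be fitted. The General overview is then incomplete, and the plan does not say how those participants enter the GM+M vs UM comparison.

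**Working it through.** **Inputs.** From Power and Sample size: 28% vs 13% abstinence, type 1 error 5%, 80% power, 123 per group in 4 groups (492), 20% attrition; framing main effect of +11 points from 14 to 17%. From General overview: N=367 and two arms. Assumptions: two-sided test, equal allocation, and no adjustment for the stated ICC of 0.85, whose formula is not given.

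**1. The plan's own figure.** The two-proportion sample size with continuity correction is 126 per group (113 without), close to 123. At 123 per group, power is 79% with the correction and 83% without. For attrition, 123/0.8 = 153.75, rounded up to 154; 4 x 154 = 616, the Human Subjects figure. Two arms would give 2 x 123/0.8 = 307.5, or 308. The current 367 matches neither.

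**2. Estimability.** Columns are [intercept, framing, NRT].

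- Two arms: the rows are (1,0,0) and (1,1,1). Rank is 2 of 3, or 2 of 4 with the interaction. Adding site and motivation stratum gives 5 of 6, so the deficiency remains.
- The contrasts (0,1,0) and (0,0,1) lie outside the row space: neither component is estimable. The contrast (0,1,1), the package, lies inside it.
- Four cells: rank is 3 of 3, or 4 of 4 with the interaction, and every effect is estimable.

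**3. Worked example at the planned rates.** 51/183 in GM+M (28%) and 24/184 in UM (13%).

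- One indicator: OR = (51 x 160)/(132 x 24) = 2.58. The SE of the log OR is √(1/51 + 1/132 + 1/24 + 1/160) = 0.274, so the 95% CI is 1.51 to 4.41.
- Both terms, GEE in Python's statsmodels: OR 1.60 (1.23 to 2.10) for framing and the same for NRT, without warning. This is √2.58, half the log OR given to each. Any other split fits equally well.
- Both terms, logistic and Cox routines in the same library: both stop with a singular-matrix error.

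**4. Power under each reading at N=367.** Power = Φ{[|p₂−p₁| − 1.96√(2p̄(1−p̄)/n)] / √[(p₁q₁+p₂q₂)/n]}, without continuity correction. The documents do not say whether the planned rates refer to completers, so loss is handled in two ways: 20% dropped, or 20% counted as smoking (rates multiplied by 0.8, giving 22.4% vs 10.4% for the primary contrast).

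| Comparison | No loss | 20% dropped | 20% as smoking |
|---|---|---|---|
| Package vs neither, two arms (183.5 each) | 95% | 89% | 88% |
| Package vs neither, balanced 2x2 (91.75 per cell) | 71% | 62% | 59% |
| Framing main effect, 25% vs 14% (183.5 per margin) | 76% | 66% | 64% |
| Framing main effect, 28% vs 17% (183.5 per margin) | 72% | 62% | 59% |

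At 246 per margin (N=492) the framing main effect has 87% and 83% power, so the claim of more than 80% fits the four-group N=492 and not N=367.

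**5. If a few people were in single-factor arms.** Their number is not given, so this is illustration only. Assume each component carries half the package log OR (0.957/2) and N stays at 367. With 10, 20, 30 or 50 people in each single-factor cell, power for one component is about 13%, 20%, 27% or 36%.

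**The case against.** The primary comparison is stated consistently, and a competent analyst would fit one indicator. What fails is the component claims, some of them in background text. This stands, and the finding does not threaten the primary result. But the two-term sentence explicitly covers the primary models, and Specific Aims claims power for main effects, so it is more than leftover rationale.

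The documents do not prove that a singular fit would occur. This is Version 13, and participants may have been randomised to four arms earlier. That is also true, so the consequence is conditional on the allocation. Text must change either way: no reading leaves the two-arm overview, the two-factor models and the power statement all correct.

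Some wording does not help to settle the design. The references to a gain-framed group under Intake and Consent, and to a group without NRT under VA medication dispersal, also fit two arms.

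The software output is one library's behaviour on a simplified example without site or repeated visits. It shows non-identifiability and does not predict the trial's result. Continuity correction lowers the power figures: 93, 86 and 85% for two arms, and 65, 54 and 51% for the 2x2 primary contrast. The conclusions are unchanged.

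**Conclusion.** The concern holds and should be fixed before analysis. If the two arms in the General overview cover everyone analysed, the specified models are rank-deficient, and only GM+M vs UM can be estimated. That contrast keeps 88 to 95% power at N=367 under the planned rates. Framing and NRT main effects, their interaction, and the stated power for framing are not available.

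If a balanced 2x2 is intended, the component effects are estimable. N=367 then gives 59 to 71% power for the primary contrast and 59 to 76% for the framing main effect.

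Confidence is high that the sections contradict each other. Which consequence applies depends on the allocation history, which the documents do not give.

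**What to change.** 1. State whether anyone was randomised to a framing-only or NRT-only arm, how many and when. Reconcile Specific Aims, Significance, General overview, Power and Sample size, Statistical Analysis, Human Subjects and the monitoring plan with that statement. Tidy the group wording under Intake and VA medication dispersal at the same time.
2. If nobody was, replace the two factor terms in every efficacy model with one GM+M vs UM indicator plus site, and define treatment status and treatment condition in the exploratory analyses as that indicator. Delete the 2x2, main-effect, interaction and individual-effect claims, the framing power sentence and the marginal rates. Limit conclusions to the package, and say that mediation results cannot be attributed to one component.
3. If some were, use a categorical arm variable with one level per arm used and GM+M vs UM as the pre-specified primary contrast. This keeps all randomised participants in the analysis. State how the period of randomisation is handled, and label any retained main-effect estimate with the precision the single-factor arms allow.
4. If a full 2x2 is intended, correct the General overview and restate power at N=367.

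The cost is wording and one factual statement, with no new data or participants. Under two arms, the sponsor gives up component claims that the design could not support.
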